1.7 Subject Exclusion Criteria

An individual who meets any of the following criteria will be excluded from participation in this study:

- If participant self-reports liver, kidney, heart, blood, metabolic or systemic disease which may make execution of the protocol or interpretation of the results difficult
- If participant has severe physical impairments (e.g., complete blindness or deafness) and/or cognitive impairments (e.g., dementia) that precludes participation in the procedures outlined in this proposal
- If participant is or could be pregnant
- If participant is currently receiving radiation
- If participant not able to hold mouth open for extended period of time

1.8 **Strategies for Recruitment and Retention**

Recruitment Process:

Subject candidates will be identified by screening clinic schedules for extraction treatments and reviewing the subject candidate's dental records as prescreening activities. Subject Withdrawal

1.8.1 Reasons for Withdrawal

Subject participation is strictly voluntary and there is no treatment associated with the study; therefore, a subject may withdraw from further participation in the study without penalty or harm. Any reason(s) the subject may give for terminating his or her participation will be kept

confidential. No further information will be required of the subject and the subject will be compensated for their participation undergone prior to termination.

Study personnel will be authorized to release a subject from further study participation if:

- The researcher believes that it is not in the subject's best interest to stay in the study.
- The subject becomes ineligible to participate.
- The subject's condition changes such that he or she needs treatment that is not allowed while taking part in the study.
- The subject does not follow instructions from the researchers.
- The study is suspended or canceled.

1.8.2 Handling of Subject Withdrawals

No further information will be required of the subject. Clinical data collected prior to the point of withdrawal will be used in the study. Subjects who do not complete the study will be replaced.

1.9 **Premature Termination or Suspension of Study**

This study may be suspended or prematurely terminated if there is sufficient reasonable cause. Written notification, documenting the reason for study suspension or termination, will be provided by the suspending or terminating party. If the study is prematurely terminated or suspended, the principal investigator will promptly inform the IRB and will provide the reason(s) for suspension or termination.

Circumstances that may warrant termination include, but are not limited to:

- Determination of unexpected, significant, or unacceptable risk to subjects
- Insufficient adherence to protocol requirements
- Data that are not sufficiently complete and/or evaluable
- Determination of futility

STUDY SCHEDULE

1.10 Screening

Subject candidates will be identified by screening clinic schedules for dental extraction treatments and reviewing the subject candidate's dental records. Patients that appear to qualify during the prescreening process will be contacted directly in person on the day of their regular extraction consult appointment.

1.11 Enrollment/Baseline (Day 0, visit 1)

Subject candidates will be approached at the time when they present to the dental clinic for the consultation prior to their dental extraction. Consent will be obtained when patient showed interest in participation in the study.

1.12 Study Visit (Procedure Appointment)

Study visit will take approximately 30-45 minutes. This visit includes completing study related procedures including completing the questionnaire by the participant, and performing vitality testings' including cold, EPT, percussion, palpation and pulse oximeter recordings.

1.13 Withdrawal Visit

There are many reasons why the researchers may need to end an individual's participation in the study. Some examples are:

- \checkmark The researcher believes that it is not in your best interest to stay in the study.
- ✓ You become ineligible to participate.
- \checkmark You do not follow instructions from the researchers.
- \checkmark The study is suspended or canceled.

STUDY PROCEDURES/EVALUATIONS:

1.14 **Study Procedures/Evaluations**

Study procedures will be evaluated continuously throughout this study to evaluate adherence to the protocol.

1.15 Laboratory Procedures/Evaluations

Upon completion of extraction, the teeth will be placed in formalin-containing bottle. After formalin fixation, the teeth will be prepared for histological examination using 10% EDTA for demineralization. Following that, the teeth are trimmed, embedded in paraplast and cut longitudinally to obtain 6um thick section. The sections were stained with H&E and examined with a light microscope. The histological diagnosis are based on the classification used by Seltzer et al. as follow:

- 1. Normal Pulp: Intact, uninflamed pulp
- 2. Transitional Stage: Intact pulp with scattered inflammatory cells
- 3. Pulpitis: inflammatory process affecting the coronal and radicular
- 4. Pulp Necrosis: All pulp tissue is necrotic

1.16 Study Specific Biospecimens

1.16.1 Specimen Collection Procedures

After the study related procedures are completed, dental care is transferred to the Oral Surgeon

1.16.2 Specimen Preparation, Handling, and Storage

Extracted teeth will be collected in "biohazard specimen transfer bag" and labels with their specific ID number. They will then be transferred from oral surgery on the same day to the pathology laboratory at the school of dentistry for histology.

1.16.3 Specimen Shipment

There is no shipment required for this study. All the specimen histological evaluation will be done at the dental school.

1.17 **Questionnaire Administration**

History of dental and orofacial pain will be collected in person usingvalidated questionnaires;

- 1. DePaQ (Validated Dental Pain Questionnaire)
- 2. Fibromyalgia Survey Questionnaire (FSQ)

ASSESSMENT OF SAFETY

1.18 **Specification of Safety Parameters**

Safety monitoring for this study will focus on unanticipated problems involving risks to participants, including unanticipated problems that meet the definition of an adverse event.

1.18.1 Unanticipated Problems

The Office for Human Research Protections (OHRP) considers unanticipated problems involving risks to subjects or others to include, in general, any incident, experience, or outcome that meets **all** of the following criteria:

- 7. unexpected in terms of nature, severity, or frequency given (a) the research procedures that are described in the protocol-related documents, such as the IRB-approved research protocol and informed consent document; and (b) the characteristics of the subject population being studied;
- 8. related or possibly related to participation in the research (possibly related means there is a reasonable possibility that the incident, experience, or outcome may have been caused by the procedures involved in the research); and
- 9. suggests that the research places subjects or others at a greater risk of harm (including physical, psychological, economic, or social harm) than was previously known or recognized.

1.18.2 Serious Adverse Events

An adverse event (AE) is defined as: "Any untoward or unfavorable medical occurrence in a human subject, including any abnormal sign, symptom, or disease, temporarily associated with the subject's participation in the research, whether or not considered related to the subject's participation in the research." AE reporting is explicit to any AEs with a causal relation to the study procedure (pulp testing, use of pulse oximeter). Any complications due to the standard of care extraction procedure will not be reported as these AEs are not as a result of a casual relation to the study procedure. Only AEs that occur during the investigational device testing would be reported. An adverse finding can include a significant change in baseline symptoms, abnormal assessments or any combination of these.

Examples of AEs are as follows:

- Changes in the general condition of the patient
- Subjective symptoms offered by or elicited from the patient
- Objective signs observed by the Investigator or other study personnel

• All concurrent diseases that occur after the start of the study, including any change in severity or frequency of preexisting dental pain.

Any participant that has an adverse event will be followed weekly until either the event has resolved or the event is considered stable by the participant and the research team. Adverse events that persist for an extended duration (such as over the duration of the study) will also be followed weekly until either the event is resolved or considered stable by the PI and the research participant.

1.19 **Reporting Procedures**

All adverse events, regardless of attribution, will be recorded by the Principal Investigator (PI) and/or a study team member in the patient's research file using the AE CRF. In addition, AEs will be tracked in aggregate using the AE tracking log. This log will also document corrective actions required and attribute severity, relatedness and expectedness.

The PI will review and acknowledge (by signing the CRF) all recorded adverse events. The U-M IRB will receive at least an annual summary of all AEs in aggregate. AEs will be reported within 7-days of the occurrence notification. Unanticipated problems or privacy violations/breach of confidentiality will be treated as serious and also reported within 7-days of occurrence to the appropriate oversight body.

STUDY OVERSIGHT

The PI retains primary responsibility for oversight. In addition, the Institutional Review Board of the University of Michigan will review and approve the protocol, study procedures and continuing reviews.

Study staff will permit authorized representatives and regulatory agencies to examine (and when required by applicable law, to copy) research records for the purposes of quality assurance reviews, audits, and evaluation of the study safety, progress and data validity.

CLINICAL SITE MONITORING

Because the study meets IRB approval, it is continually reviewed by IRB. This study is cross sectional and does not involve administration of any clinical treatments. The study involves no more than minimal risk to participants. For these reasons, it is our belief that additional monitoring of the site is not necessary.

STATISTICAL CONSIDERATIONS

1.20 Study Hypotheses

The calculations are based on a comparison of the test results and "true" disease status. The sensitivity, specificity, and positive and negative predictive values of heat and cold application and electrical pulp tests will be calculated. Teeth are grouped into two categories, healthy, true disease (irreversible pulpitis and necrosis). A perfect diagnostic test would always be positive in the presence of disease and negative in the absence of disease. Therefore, sensitivity, specificity, and positive and negative predictive value have been developed to characterize test accuracy and to compute the benefits of test usage. In addition to that, clinical measurements of the extracted teeth will be compared with identification of the true disease by histological evaluation for the pulp status.

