1.3.2 Potential Benefits

Participants are not expected to receive any personal benefits from being in this study.

OBJECTIVES

1.4 **Study Objectives**

The purpose of this study is to assess tooth health by using a pulse oximeter which measures the blood flow within the tooth. We hypothesize that if we can measure both sensation and blood flow in a tooth, we will be able to better determine if the tooth is "alive or dead". In the future, this method may help determine which teeth are diseased and require dental treatments.

Our specific aims are:

Aim - 1: To measure pulpal blood flow using pulse oximeter and Laser Doppler Flowmeter

Aim - 2: To measure tooth vitality using Cold, Electrical Pulp tester (EPT) , percussion and palpation testing

Aim - 3: To assess histological presentation of the pulp the extracted teeth

Aim - 4: To evaluate the relationships between the Aims 1-3 to determine if pulpal blood flow is a reliable indicator of tooth vitality.

1.5 **Study Outcome Measures**

Primary Outcomes Measures: Correlation Between Subjective and Objective Measurements of Pulpal Status

- Subjective Measurements Pulpal Status: Conventional pulpal diagnosis using cold test [Endo Ice, Coltene/Whaledent, Cuyahoga Falls, OH, USA] and Electrical Pulp Test -EPT S[Kerr Vitality Scanner, SybronEndo] testing and recorded, along with vertical and lateral percussion and palpation responses. Conventional pulpal diagnosis assessment would be used for teeth that are planned for extraction and additional teeth (10 total) in each participant
- *Objective Measurements Pulpal Status:* Measurements obtained from pulse oximeter gives a series of reading of oxygen saturation level, and pulse. Pulse oximeter measurements would be used for teeth that are planned for extraction and also up to 2-5 additional teeth in each participant

Exploratory Outcomes:

- *Systemic Vital Sign Measurements:* Blood pressure and pulse recording will be obtained from the recorded values from the participant's chart.
- *Histological Assessment of the Extracted Teeth:* Upon completion of extraction, the teeth will be placed in formalin-containing bottle. After formalin fixation, the teeth will be prepared for histological examination using 10% EDTA for demineralization. Following that, the teeth are trimmed, embedded in paraplast and cut longitudinally to obtain 6um thick section. The sections were stained with H&E and examined with a light microscope.

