1.22 Final Analysis Plan

To compare accuracy of pulp vitality between traditional tooth vitality testing (Cold and EPT) to pulse oximeter reading to determine if the pulse oximeter is a reliable indicator of tooth vitality. We will analyze the relationships between these clinical readings using Pearson correlations and/or Chi Square tests. We will evaluate repeatability of the measurements within a tooth for the pulse oximeter using Bland-Altman plots, intraclass correlation coefficients (ICCs), and the percentage of repeat measurements within +/- 0.5 mm along with a 95% confidence interval for the percentage. Pulse oximeter reading will be compared against the gold standard (Cold and EPT) assessment using paired t-tests, 95% confidence intervals for the difference from the gold standard with a 95% confidence interval. The clinical pulpal status will be compared to the histological status for the difference using ANOVA and compared for the percentage of measurements with +/- gold standard visual assessment of the pulp status using McNemar's tests.

SOURCE DOCUMENTS AND ACCESS TO SOURCE DATA/DOCUMENTS

Study staff will maintain appropriate dental and research records for this study. Study staff will permit authorized representative and regulatory agencies to examine (and when required by applicable law, to copy) research records for the purposes of quality assurance reviews, audits and evaluation of the study safety, progress and data validity.

QUALITY CONTROL AND QUALITY ASSURANCE

Quality control will be continually monitored by periodic (semi-annual) reviews of the protocol and procedures used in the study. All questionnaire data is reviewed on the day of the participant visit for completeness. De-identified data is monitored after collection for various points of quality assurance.

ETHICS/PROTECTION OF HUMAN SUBJECTS:

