1.30 Data Capture Methods

Data will be kept confidential, in part, by assigning each participant an ID number. This number will be used to keep track of each individual's data. Participant names will never be collected or stored with research data. Paper copies of the data from questionnaires and radiographic copy of each participant will be stored in a locked file cabinet in a locked office. Paper copies of the consent document and the payment processing forms (i.e. those containing subject names) will be stored in a separate locked filing cabinet away from the data. The PI (or a designee) will retain the keys to access these files.

Participants will complete paper-based questionnaires; no electronic survey completion will occur. Data will be verified and checked for completeness and initialed by the principle investigator prior to the completion of the visit. All data will be entered into a research database, REDCap and/or excel.

Study data will be collected and may be managed using an electronic data capture tools hosted at University of Michigan. REDCap (Research Electronic Data Capture) is a secure, web-based application designed to support data capture for research studies, providing: 1) an intuitive interface for validated data entry; 2) audit trails for tracking data manipulation and export procedures; 3) automated export procedures for seamless data downloads to common statistical packages; and 4) procedures for importing data from external sources.

1.31 **Types of Data**

Outcome measure data of cold testing, EPT, percussion, palpation testing and pulse oximeter reading will be collected in the study. Extracted teeth that meet the inclusion criteria will be also collected for histological evaluation.

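### Sections 1.20 and 1.22 plan accuracy figures for an untested heat stimulus but none for the pulse oximeter, name the reference standard inconsistently, and compare oximeter with Cold/EPT by a paired t-test that cannot measure agreement

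*Combined protocol and SAP*

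**What the plan says.** Section 1.20 groups teeth by disease: "Teeth are grouped into two categories, healthy, true disease (irreversible pulpitis and necrosis". It assigns the four accuracy measures as follows: "The sensitivity, specificity, and positive and negative predictive values of heat and cold application and electrical pulp tests will be calculated". It adds that "clinical measurements of the extracted teeth will be compared with identification of the true disease by histological evaluation for the pulp status".

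Section 1.22 opens with its purpose: "To compare accuracy of pulp vitality between traditional tooth vitality testing (Cold and EPT) to pulse oximeter reading". It names Pearson correlation and/or chi-square for the relationships between the clinical readings. It then says: "Pulse oximeter reading will be compared against the gold standard (Cold and EPT) assessment using paired t-tests", with a confidence interval for the difference. Its last sentence turns to histology: "The clinical pulpal status will be compared to the histological status for the difference using ANOVA", and adds McNemar tests against a gold-standard visual assessment of the pulp.

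On the data, section 1.31 says: "Outcome measure data of cold testing, EPT, percussion, palpation testing and pulse oximeter reading will be collected in the study". Section 1.5 describes the oximeter output: "Measurements obtained from pulse oximeter gives a series of reading of oxygen saturation level, and pulse". The Study Design section describes cold and EPT as ending when the participant reports a sensation, and the oximeter as detecting whether a pulse is present.

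Section 1.5 makes the correlation of subjective with objective measurements the primary outcome and lists histology as exploratory. Aim 4 asks whether pulpal blood flow is a reliable indicator of vitality.

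**The concern.** Four things do not fit together.

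- Heat is down for accuracy analysis, but there will be no heat data.
- Section 1.20 presents sensitivity, specificity and predictive values as the way to characterise a test, then assigns them to the comparators and not to the device.
- Cold/EPT is a competitor to be judged in section 1.20 and in the opening of section 1.22, and a reference two sentences further on. When a competitor is also the reference, every disagreement counts as an oximeter error, so the oximeter cannot be shown to be the better test.
- The paired t-test looks at a mean difference, which says nothing about whether the two tests agree tooth by tooth.

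At stake is Aim 4 and the opening question of section 1.22. A report that followed the plan to the letter would give accuracy for cold and EPT, none for the oximeter, and a p-value that does not bear on reliability.

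**Working it through.** The plan has no figure to reproduce here. Section 1.21 gives 35 completers without inputs and no number of teeth. The textual checks come first. All numerical inputs after them are assumed, and they show mechanism only.

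**Heat.** The procedures, the aims, the visit description (1.12), the data list (1.31) and Form 2 contain cold, EPT, percussion, palpation and the oximeter, and most add the laser Doppler flowmeter. None contains a heat test. Among study activities, heat appears only in a symptom question and in inclusion criterion 7 on pain history.

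**Reference standard.** Section 1.20 judges cold and EPT against true disease and ties that to histology for extracted teeth. Section 1.22 gives the gold-standard label to Cold/EPT, then to a visual assessment in the sentence on histology. That is two references under one name.

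**Disease grouping.** Section 1.20 counts irreversible pulpitis and necrosis as disease. Section 1.15 has four classes: normal, transitional, pulpitis and necrosis. Pulpitis is not split into reversible and irreversible, and transitional is not assigned to a group.

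**Paired t-test, different scales.** Assume 20 teeth: 10 respond to cold (coded 1) and 10 do not (coded 0). Assume oximeter readings of 90 or 70, ten of each. The mean paired difference equals the difference of the two means, 80 − 0.5 = 79.5, however the readings are matched to teeth. Only the SD changes; t = mean/(SD/√20).

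| Oximeter against cold | Differences | SD | t | 95% CI |
|---|---|---|---|---|
| Full agreement | 89 ×10, 70 ×10 | 9.75 | 36.5 | 74.9–84.1 |
| Full reversal | 69 ×10, 90 ×10 | 10.77 | 33.0 | 74.5–84.5 |
| No relation | 89, 69, 90, 70 ×5 each | 10.27 | 34.6 | 74.7–84.3 |

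All three give p < 0.001. With saturation recorded as a proportion, the mean difference becomes 0.80 − 0.50 = 0.30 on the same data.

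**Paired t-test, both coded 0/1.** The mean difference is now the difference of two marginal proportions. Under full reversal there are ten differences of −1 and ten of +1, so the mean is 0, t = 0 and p = 1. Complete disagreement looks like no difference.

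**Chi-square.** Under full reversal the 2×2 table has 0 and 10 in the first row, 10 and 0 in the second. Chi-square is 20 without continuity correction and 16.2 with it, p < 0.001 either way, exactly as under full agreement. It shows association only. Kappa separates the two cases: under reversal observed agreement is 0 and expected agreement 0.5, so kappa = (0 − 0.5)/(1 − 0.5) = −1.

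**Cold/EPT as reference.** Let the oximeter have true sensitivity and specificity 0.95, let Cold/EPT have sensitivity 0.75 and specificity 0.85, let prevalence be 0.3, and let errors be independent given disease. Apparent oximeter sensitivity is (0.3×0.95×0.75 + 0.7×0.05×0.15)/(0.3×0.75 + 0.7×0.15) = 0.219/0.330 = 0.66. Over Cold/EPT sensitivity 0.75–0.95, specificity 0.85–0.95 and prevalence 0.3–0.5, the combinations tried give apparent sensitivity 0.66–0.91 and apparent specificity 0.75–0.93, all below the true 0.95.

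**Precision against histology.** Exact 95% intervals are 44–98% for 8/10 and 56–94% for 16/20, before allowing for clustering.

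**Predictive values.** With sensitivity 0.80 and specificity 0.90, PPV/NPV are 0.67/0.95, 0.89/0.82 and 0.97/0.53 at prevalence 0.2, 0.5 and 0.8. They describe only the teeth collected.

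**The case against.** The strongest reply is that the plan does more than the accuracy list suggests. Section 1.20 compares clinical measurements of extracted teeth with histology, section 1.5 lists oximetry as the objective measure of pulpal status, and section 1.22 opens with the oximeter's accuracy. This stands: a comparison of the oximeter with histology is planned on the natural reading, and a reader who inferred that there is none would be wrong. But the methods named for it are ANOVA and McNemar. Neither yields sensitivity or specificity, and McNemar needs a positive/negative result that is not defined.

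A second reply is that presence of a pulse already supplies the rule. It suggests one, but the same device also yields saturation and no section states which result counts as positive. If pulse presence and cold response are both 0/1, the charge of unlike units falls away; the t-test still sees only marginal proportions.

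Third, Cold/EPT can be applied to every tested tooth and histology only to extracted ones, so two references are understandable. That explains the usage but does not reconcile it. Nor do the documents support the inference that Cold/EPT replaces histology throughout, since section 1.22 also gives the label to the visual assessment.

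A reader might also infer that a cut-off will be picked from the data. With assumed tooth counts and a worthless continuous reading, the best cut-off would show an average sensitivity + specificity − 1 of 0.19 to 0.26. No section plans this, so it is a reason to fix the rule and not a fault of the plan.

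**Conclusion.** The point holds and should be fixed. The heat entry has no data behind it, the device is missing from the accuracy list, the reference standard is inconsistent, and the paired t-test is uninformative under either coding. That it ignores the matching of readings follows from algebra and does not rest on the assumed values. The figures 79.5 and 0.30 do rest on them and are not effect sizes for this study.

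A reader might conclude that the primary outcome fails. It does not: the correlation in section 1.5 is served by the Pearson and chi-square analyses. What goes unanswered is whether the oximeter is a reliable indicator of vitality beside Cold/EPT. How precisely histology could answer that is unknown, because the documents give no number or case mix of collected teeth.

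**What to change.** 1. In section 1.20, remove heat or reconcile it with the procedures, and add the pulse oximeter to the tests given sensitivity, specificity, PPV and NPV.
2. In section 1.22, call Cold/EPT the comparator and reserve gold standard for histology. Delete the paired t-test and its interval for the difference. Keep Pearson and chi-square as measures of association; if agreement is wanted, report percent agreement or kappa on binary results.
3. Estimate the accuracy of oximeter, cold and EPT against histology in the same tested, extracted teeth. Use one oximeter positivity rule fixed before analysis, for example pulse present or absent. ROC/AUC may be added for continuous saturation but does not replace the rule. Give 95% intervals that allow for teeth clustered within participants, for example a bootstrap by participant. Label this exploratory, and limit PPV and NPV to the prevalence among collected teeth.
4. Reconcile the disease grouping in section 1.20 with the four classes in section 1.15, stating where transitional and pulpitis fall.

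The cost is text edits, a matching definition of the Pulse Ox field on Form 2, and analysis of data already planned. No visit or procedure is added. The downside is that only tested extracted teeth that are collected contribute, so intervals will be wide.

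### Section 1.20 scores tests against healthy versus pulpitis plus necrosis, which does not measure accuracy for vitality; a necrosis contrast (class 4 versus classes 1-3) should be prespecified

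*Combined protocol and SAP*

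**What the plan says.** Section 1.20 states the reference for the accuracy measures: "Teeth are grouped into two categories, healthy, true disease (irreversible pulpitis and necrosis". It sets the standard that "A perfect diagnostic test would always be positive in the presence of disease and negative in the absence of disease". It assigns sensitivity, specificity and predictive values to heat, cold and EPT, and does not name the pulse oximeter. It then adds that "clinical measurements of the extracted teeth will be compared with identification of the true disease by histological evaluation for the pulp status".

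The stated question elsewhere is vitality. Section 1.4 frames the hypothesis as whether a tooth is alive or dead, and Aim 4 is "to determine if pulpal blood flow is a reliable indicator of tooth vitality". Section 1.22 sets out to "determine if the pulse oximeter is a reliable indicator of tooth vitality". The Study Design section introduces cold, EPT and percussion as alive/dead tests and gives the same purpose for examining the extracted teeth. Disease is also a target: section 1.4 says that "this method may help determine which teeth are diseased and require dental treatments", and section 1.1 mentions inflammatory status.

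Section 1.15 records histology in four classes: 1 normal, 2 transitional (intact pulp with scattered inflammatory cells), 3 pulpitis, 4 necrosis. Only class 4 is defined as wholly necrotic.

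Section 1.22 uses a different reference for the oximeter: "Pulse oximeter reading will be compared against the gold standard (Cold and EPT) assessment". It also plans an ANOVA and McNemar's tests of clinical against histological status, without saying how the four classes enter. Section 1.5 lists histology as exploratory; the primary outcome is the correlation between subjective and objective measurements.

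**The concern.** There are two targets, vitality and disease, and one written dichotomy. Pooling pulpitis with necrosis is legitimate for disease. It is not a vitality reference, because an inflamed pulp can be alive. Under the 1.20 standard, an alive/dead test that correctly calls such a tooth alive is charged with missing disease. Its sensitivity would then describe the mix of extracted teeth as well as the test, and an accurate vitality test could look poor.

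The reference is also incompletely defined:

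- Irreversible pulpitis is not one of the four classes in section 1.15, and class 2 is assigned to neither group.
- The oximeter, the device under study, is left out of the accuracy measures in 1.20.
- Section 1.22 calls cold and EPT the gold standard although 1.20 identifies true disease by histology. Its last sentence refers to a further, visual gold standard that it does not define.

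Without a rule set in advance, the reference could be chosen after the histology is known.

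**Working it through.** **Plan's own figure.** There is none to reproduce. Section 1.21 gives 35 completers without derivation. No section gives the number of teeth with histology or their class mix, so every tooth count below is an assumption.

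**Inputs.** The classes come from section 1.15. Let n1 to n4 be the numbers of extracted teeth in classes 1 to 4. Assume that the 1.20 groups are histological (disease = classes 3 and 4, healthy = classes 1 and 2), that every class 3 pulp is vital, and that teeth are independent. A perfect vitality test is positive ('dead') on class 4 only.

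**Formulas.**

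- Sensitivity against the pooled reference: n4/(n3 + n4).
- Sensitivity against class 4 versus classes 1-3: n4/n4 = 100%, with exact (Clopper-Pearson) lower 95% limit 0.025^(1/n4).
- Pooled sensitivity if class 2 is also counted as diseased: n4/(n2 + n3 + n4).

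**Results**, with n3 + n4 = 20 and n2 = 5 assumed:

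| n3 | n4 | Pooled sensitivity (exact 95% CI) | Class 4 sensitivity (exact 95% CI) | Pooled, class 2 as diseased |
|---|---|---|---|---|
| 15 | 5 | 5/20 = 25% (9% to 49%) | 5/5 (48% to 100%) | 5/25 = 20% |
| 10 | 10 | 10/20 = 50% (27% to 73%) | 10/10 (69% to 100%) | 10/25 = 40% |
| 5 | 15 | 15/20 = 75% (51% to 91%) | 15/15 (78% to 100%) | 15/25 = 60% |

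If class 2 is counted as healthy, the denominator stays 20 and pooled sensitivity does not change.

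**The converse.** A perfect disease test, positive on classes 3 and 4, scored against class 4 has specificity (n1 + n2)/(n1 + n2 + n3). With assumed mixes (n1/n2/n3/n4) of 15/5/10/5 and 10/5/15/5, this is 20/30 = 67% and 15/30 = 50%. One contrast cannot serve both targets, so both are needed.

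**Precision of the added contrast.** If every class 4 tooth is called correctly, the lower 95% limit is 29% with 3 teeth, 40% with 4, 59% with 7, 69% with 10 and 77% with 14. Several teeth from one participant would widen these intervals.

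**The case against.** Section 1.20 announces disease as its target, and a disease reference is right for a disease analysis. It names heat, cold and EPT, whereas Aim 4 is about pulpal blood flow. The comparisons that bear on Aim 4 are in section 1.22, where the ANOVA and McNemar's tests could use all four classes. The 1.20 groups might also be clinical diagnoses: irreversible pulpitis is not a histological class, and the histology comparison is introduced as an addition. Alive/dead scoring is not the only option either, since section 1.5 speaks of conventional pulpal diagnosis and no positivity rule is written. Finally, the percentages restate an assumed mix.

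Most of this stands as a limit on the claim. A reader might infer that the plan cannot answer Aim 4. The documents do not support that: the fault is shown for the 1.20 table, the four classes are recorded, and 1.22 leaves its histology levels open. A reader might also infer that the oximeter's accuracy will be understated by a known amount. That fails too, because 1.20 computes no accuracy for the oximeter and the mix is unknown.

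The objection does not remove the gap. Cold and EPT, which 1.20 does score, are described as alive/dead tests. No section specifies a contrast of class 4 with classes 1-3. As written, the comparisons in 1.22 yield no sensitivity or specificity for vitality. The histological reading of the groups is the likelier one, because the same section has true disease identified by histology. If the grouping is clinical, the plan has no stated binary histological reference at all.

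**Conclusion.** The point holds in a limited form. The 1.20 table does not measure vitality accuracy, and the 1.22 comparisons as written do not supply it. On the histological reading with alive/dead scoring, any vital pulpitis tooth lowers the apparent sensitivity of a correct vitality test. The direction does not depend on the assumed counts, but the size does: 25% to 75% is an illustration, not an estimate for this trial.

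Independently of any counts, the 1.20 groups do not map to the four classes in 1.15, the oximeter has no planned accuracy measures in 1.20, and the gold standard in 1.22 conflicts with histology as the identifier of true disease.

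The reach is the exploratory histology analysis and, through it, part of the evidence for Aim 4. The change should be made, but the point does not invalidate the study.

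**What to change.** For extracted teeth with histology:

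- Add to sections 1.20 and 1.22 a prespecified vitality reference of class 4 versus classes 1-3, and state where a partly necrotic pulp is classed.
- Report sensitivity, specificity, PPV and NPV with exact intervals for cold, EPT and the pulse oximeter, with LDF as exploratory. Allow for several teeth per participant in the intervals, or state that independence is assumed.
- Have the investigators set each test's 'dead' rule before histology is seen. For the oximeter, the rule should say whether it uses pulse, saturation or both.
- Keep healthy versus disease as a separately labelled analysis. State how the four classes map to it, and show results with class 2 placed each way.
- Use histology as the accuracy reference, and treat the oximeter versus cold and EPT comparison in 1.22 as agreement between tests. Teeth that are not extracted have no histology and should stay out of the accuracy figures.

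The cost is mainly wording, since the histology and its four classes are already planned. Forms 2 and 3 show no field for the histological class, so one may need adding. The drawback is precision: with only 3 class 4 teeth, a perfect 3/3 still gives 29% to 100%. Fixing the contrast in advance does not cure that, but it prevents a choice of reference after the results are seen.
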